# of tablets used between Vi and Vj = (# tablets dispensed at Vi) - (# tablets returned at Vj) - (# tablets unaccounted for at Vj)

The average dose of rescue medication per day while on study drug (g/day) will be determined as

total dose of rescue medication used (g) number of days on study drug

where,

 $number of days on study drug = \{ \begin{array}{ll} duration of exposure, \\ duration of exposure - 1, \end{array} if trt end date < V6 account date \\ if trt end date = V6 account date \\ \end{array} \}$ 

Note: a consistent approach to determining 'number of days on study drug' is taken across exposure, compliance and rescue medication calculations.

The time between baseline and first intake of rescue medication (days) will also be determined as

Date of first intake of rescue medication - treatment start date

For subjects that have first intake of rescue medication on the Visit 2 (treatment start) date, the time to first intake of rescue medication will be set to 0.5 days.

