#### **Rescue Medication (paracetamol/acetaminophen)**

The total dose of rescue medication (g) taken will be determined as

total # of tablets of rescue medication used  $\times 0.5$ 

where,

total # of tablets used = (#of tablets used between V2 & V4) + (#of tablets used between V4 & V6)

and

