#### 4.2.2.2 Summary presentations and methods of analysis

All summaries and statistical analysis for the secondary endpoints will be performed for the mITT set only.

For the following continuous secondary endpoints, absolute values and absolute change from baseline will be summarised over time by treatment group. Statistical analysis and hypothesis testing will be conducted as for the primary efficacy analysis using a mixed effects repeated measures model with data from double-blind treatment groups only.

- WOMAC total score
- WOMAC function score
- WOMAC stiffness score
- WOMAC pain weight bearing score
- WOMAC pain non-weight bearing score

- Patient Global Assessment (PGA)
- ICOAP total OA pain score
- ICOAP constant OA pain score
- ICOAP intermittent OA pain score
- Chair stand test, number of repetitions

The number of subjects using any rescue medication (i.e. at least one tablet), the total dose of rescue medication (g), and the average dose of rescue medication per day on study drug (g/day) will be summarized by treatment group. Time to first use of rescue medication will be summarised by unadjusted Kaplan Meier estimates of median time to first use of rescue medication with 95% CI. For subjects not taking any rescue medication, the total dose of rescue medication will be set to 0 mg and time to first use of rescue medication will be censored at the Visit 6/EOT visit date or the last date of subject participation in the study if this is not available.

The average dose of rescue medication per day on study drug will analysed using an analysis of covariance model with treatment, sex, baseline target knee WOMAC pain sub-score, country and subject characteristic of baseline unilateral/bilateral knee OA as explanatory variables. Least square mean estimates of each dependent variable along with 95% confidence intervals (CI) will be presented for each treatment group. Estimated treatment differences between all treatment groups along with associated 95% confidence intervals and p-values will be presented.

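### The average daily rescue dose counts tablets up to the final tablet account but divides by gel days only, so it is too high for subjects who stop the gel early and take rescue before the count

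*SAP*

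**What the plan says.** SAP 4.2.2.1, Rescue Medication, builds the measure in three steps.

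- **Tablets.** The total runs from Visit 2 to Visit 6: "total # of tablets used = (#of tablets used between V2 & V4) + (#of tablets used between V4 & V6"). Each interval is a pill count, "of tablets used between Vi and Vj = (# tablets dispensed at Vi) - (# tablets returned at Vj"), less tablets unaccounted for at the closing visit. The count therefore closes on the date the tablets are accounted for.
- **Dose.** Tablets are multiplied by 0.5 g.
- **Average per day.** The ratio is introduced by "The average dose of rescue medication per day while on study drug (g/day) will be determined as". Total grams are divided by the number of days on study drug. That number is the duration of exposure "if trt end date < V6 account date", and the duration of exposure minus 1 "if trt end date = V6 account date". A note says the same day count serves exposure, compliance and rescue.

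SAP 4.2.2.2 summarises total dose descriptively and takes the per-day value into the model: "The average dose of rescue medication per day on study drug will analysed using an analysis of covariance model", with treatment differences, confidence intervals and p-values. The analysis set is the mITT. Under SAP 3.2 an early gel stopper stays in that set given a baseline and one later WOMAC pain score.

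**The concern.** Gel use ends when treatment ends, so a day count based on exposure suits gel compliance. Paracetamol use can continue after the gel stops. Nothing in the derivation cuts the tablet count at the last gel application, so for an early stopper the numerator can span a longer period than the denominator. The result is then not a dose per day on study drug, although it carries that label.

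The per-day average is the only rescue-dose variable tested between arms; the listed secondary endpoint, total dose, is only summarised. Values inflated for some subjects feed directly into the least-squares means and p-values of that test.

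**Working it through.** The plan states no numerical result for grams per day, so there is no figure of its own to reproduce. The check applies the SAP rule to explicit cases.

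**Inputs**
- Tablet window, 0.5 g per tablet and the two-branch day count: SAP 4.2.2.1.
- Remaining tablets are collected at Visit 6, planned day 29: SAP Table 1 and its note 12.
- Assumed: duration of exposure is counted inclusively from day 1, as the minus 1 in the second branch implies.
- Assumed for illustration: constant rescue use of 1.0 g/day while tablets are in hand.

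**Formula.** Let *E* be the last gel day, *A* the day of the final tablet account and *D* the SAP divisor, with *D* = *E* if *E* < *A* and *D* = *E* − 1 if *E* = *A*. The counted period is *A* − 1 days. In general the excess is (tablets taken between last gel and count × 0.5 g) / *D*. Under constant use at rate *r*, the SAP value is *r* × (*A* − 1) / *D*.

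**Completers, counted on day 29**
- Last gel on day 29: *D* = 29 − 1 = 28, and 28/28 = 1.00.
- Last gel on day 28: *D* = 28, and 28/28 = 1.00.

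The rule works in both cases.

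**Early stoppers**

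| Last gel day | Tablets counted on day | Counted days | Divisor | Factor |
|---|---|---|---|---|
| 8 | 9 | 8 | 8 | 1.00 |
| 8 | 11 | 10 | 8 | 1.25 |
| 8 | 15 | 14 | 8 | 1.75 |
| 8 | 29 | 28 | 8 | 3.50 |
| 14 | 29 | 28 | 14 | 2.00 |
| 22 | 29 | 28 | 22 | 1.27 |

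In the fourth row the gap is 28 − 8 = 20 days. The excess is 20 × 1.0 / 8 = 2.5 g/day, and 1.0 + 2.5 = 3.5.

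**Arm means at a true 1.0 g/day in every arm.** With a share *p* stopping and inflation factor *f*, the arm mean is 1 + *p*(*f* − 1). The shares are assumptions.
- Equal stopping, 10% in each arm, day-8 stop, count on day 29: 1 + 0.10 × 2.5 = 1.25 in both arms; difference 0.
- Stopping 5% versus 15%, day-8 stop, count on day 29: 1.125 versus 1.375; false difference 0.25 g/day.
- The same shares with the count on day 15: 0.10 × 0.75 = 0.075 g/day; on day 11: 0.10 × 0.25 = 0.025; on day 9: 0.
- The same shares, day-14 stop, count on day 29: 1.05 versus 1.15; false difference 0.10 g/day.

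**With matched periods.** Dividing by *A* − 1 returns 1.00 in every row of the table and leaves completers at 28 days.

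**The case against.** The strongest reply is that the first branch was written for completers. Morning gel is applied on site at Visit 6 (Protocol Table 2), so a completer's last gel falls on that date or, if that application is missed, on the evening before. The two branches bring both cases to 28 days. A reader might infer from the first branch that the SAP expected subjects to stop gel and stay until day 29; the text does not show that. This stands, but the same branch also catches every earlier stopper, and for them no tablet cut-off is given.

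Second, SAP 4.2.2.2 mentions a Visit 6/EOT date for censoring, which suggests that some early stoppers return tablets sooner. That shortens or removes the gap. The timing is not in the documents supplied, where the protocol is the synopsis and schedule only. This too stands, so the size is conditional and large individual values are not the expected case. For example, 2 g/day over 28 days with gel stopped after 7 days gives 56/7 = 8.0 g/day, above the 4 g/day maximum in the protocol synopsis. That needs a subject who stops in week 1, remains to day 29, is counted only then and keeps up that use throughout.

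Third, one common day count was a deliberate choice, and SAP 4.2.2.2 allows alternative analyses if assumptions fail. Neither resolves the point: consistency with gel compliance does not align the tablet period, and the clause concerns the assumptions of an analysis rather than how a variable is derived.

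**Conclusion.** The mismatch is in a stated rule and holds for any subject who stops the gel before the final tablet account and takes rescue in between. For those subjects the value can only be too high. Under constant use after a day-8 stop, the factor runs from 1.0 to 3.5 as the count moves from day 9 to day 29. How many subjects are affected, and by how much, cannot be read from the documents.

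Two stronger readings are tempting and not supported. One is that every early stopper is misstated: there is no inflation if the count falls on the last gel day or the day after, or if no tablets are taken in the gap. The other is that the rescue comparison is biased: that requires stopping, gap length or later rescue use to differ by arm, and the documents give no such difference. The 0.25 g/day figure illustrates that condition under assumed 5% versus 15% stopping and a day-29 count. Without such a difference, the effect on the ANCOVA is mainly outliers and added variance.

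The total-dose summary, time to first rescue and the primary analysis do not use this divisor and are unaffected. The change is worth making because this ratio carries the only between-arm test of rescue dose.

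**What to change.** For the rescue average only, divide total dose by the date of the final tablet account (Visit 6 or EOT) minus the treatment start date. Relabel it as average dose per day over the counted period, and use that value in the ANCOVA. Keep the existing study-drug day count for exposure and compliance. State in the SAP which date is the final tablet account for subjects who stop early.

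The cost is one derivation line and a label, best settled before unblinding. Completers' values do not change. The SAP formula already relies on an account date at Visit 6; that the equivalent date is recorded for early returns should be confirmed. The drawback is that rescue taken after stopping gel is averaged in, so the quantity is no longer specific to days on drug. Trimming the numerator instead is not feasible, because a pill count does not say on which day a tablet was taken.

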#### 4.2.2.2 Summary presentations and methods of analysis

All summaries and statistical analysis for the secondary endpoints will be performed for the mITT set only.

For the following continuous secondary endpoints, absolute values and absolute change from baseline will be summarised over time by treatment group. Statistical analysis and hypothesis testing will be conducted as for the primary efficacy analysis using a mixed effects repeated measures model with data from double-blind treatment groups only.

- WOMAC total score
- WOMAC function score
- WOMAC stiffness score
- WOMAC pain weight bearing score
- WOMAC pain non-weight bearing score

- Patient Global Assessment (PGA)
- ICOAP total OA pain score
- ICOAP constant OA pain score
- ICOAP intermittent OA pain score
- Chair stand test, number of repetitions

The number of subjects using any rescue medication (i.e. at least one tablet), the total dose of rescue medication (g), and the average dose of rescue medication per day on study drug (g/day) will be summarized by treatment group. Time to first use of rescue medication will be summarised by unadjusted Kaplan Meier estimates of median time to first use of rescue medication with 95% CI. For subjects not taking any rescue medication, the total dose of rescue medication will be set to 0 mg and time to first use of rescue medication will be censored at the Visit 6/EOT visit date or the last date of subject participation in the study if this is not available.

The average dose of rescue medication per day on study drug will analysed using an analysis of covariance model with treatment, sex, baseline target knee WOMAC pain sub-score, country and subject characteristic of baseline unilateral/bilateral knee OA as explanatory variables. Least square mean estimates of each dependent variable along with 95% confidence intervals (CI) will be presented for each treatment group. Estimated treatment differences between all treatment groups along with associated 95% confidence intervals and p-values will be presented.

The time between baseline and first use of rescue medication will be analysed using a Cox semiparametric proportional hazards model with treatment, sex, baseline target knee WOMAC pain sub-score, country and subject characteristic of baseline unilateral/bilateral knee OA as covariates. The relative hazards and associated confidence intervals for all pairwise comparisons will be estimated from the Cox model and displayed using Kaplan-Meier curves. Frequencies and rates will be presented by treatment group. Unadjusted Kaplan Meier estimates of median 'survival' time and 95% CI will be presented by treatment group, as stated above.

If the assumptions underlying any of the pre-specified analyses are not considered appropriate for any of the endpoints once data is available, then alternate analyses may be presented.

### 4.2.3 Quality of life analyses

The quality of life analyses will include data from the double-blind treatment groups only.

### 4.2.3.1 QoL endpoints

#### Work Productivity and Activity Impairment (WPAI) Questionnaire: General Health

The WPAI General Health questionnaire consists of six questions. Responses to the questions are used to derive WPAI outcomes, which are expressed as impairment percentages, with higher numbers indicating greater impairment and less productivity, i.e. worse outcomes.

The WPAI questions and derived endpoints are as follows:

#### WPAI Questions:

1 = currently employed (YES/NO)

- 2 = hours missed due to health problems
- 3 = hours missed other reasons
- 4 = hours actually worked

5 = degree health affected productivity while working (0-10 11-point NRS)

6 = degree health affected regular activities (0-10 11-point NRS)

WPAI derived endpoints	Derivation
Percent work time missed due to health	Q2/(Q2+Q4)
Percent impairment while working due to health	Q5/10
Percent overall work impairment due to health	$Q2/(Q2+Q4) + [(1-(Q2/(Q2+Q4))) \times (Q5/10)]$
Percent activity impairment due to health	Q6/10

Derived scores are multiplied by 100 to express them in percentages.

If any of the WPAI questions required to calculate a given WPAI outcome is missing, no data imputation will be performed and the WPAI outcome will be set to missing.

A note-to-file issued on 04JUN19 documents the strategy to be followed in cases where the reported total number of working hours (the sum of hours in WPAI questions 2, 3 and 4) are considered outside the expected normal range (0-70 hours/week) and thus are believed to be based on a misunderstanding of questions 2, 3 and 4. To exclude the invalid values, an algorithm will be applied to objectively select the participants for whom the more extreme values have been reported. The algorithm will **exclude the data from questions 2, 3 and 4 for all visits** for subjects that meet at least one of the following criteria:

- Report more than 70h work week at any time during the trial OR
- Report more than 60h work week at any time during the trial AND
  - Increase of more than 80% in total work hours per week from one or more previous visits, with a defined minimum reference value of 25 hours per week
  - Decrease of more than 50% in total work hours per week form one or more previous visits, with a defined minimum reference value of 25 hours per week.

The algorithm will be applied prior to unblinding, to ensure unbiased analysis of the valid data only. The data from the WPAI questionnaire not affected by the total number of hours reported (i.e. questions 1, 5 - if applicable - and 6) will not be excluded from analysis.

The WPAI is assessed at baseline and weeks 1, 2 and 4.

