**Secondary endpoints (double-blind treatment group only):**

- Changes from baseline in WOMAC total score and the WOMAC function and stiffness scores at week 4
- Changes from baseline in constant and intermittent OA pain assessed by ICOAP scores at week 4
- Changes from baseline in WOMAC pain weight-bearing score (questions 1, 2, and 5) and non-weight bearing score (questions 3 and 4) at week 4
- Changes from baseline in physical function assessed by the chair-stand test at week 4
- OMERACT-OARSI responder rate at week 4
- Total dose of rescue medication calculated as the sum of tablets used, based on pill counts
- Time between baseline and first use of rescue medication
- Change from baseline in WOMAC pain sub-score (questions 1 to 5) between groups receiving AMZ001 QD and BID in the target knee as evaluated at week 4
- Changes from baseline in constant and intermittent OA pain assessed by ICOAP scores between groups receiving AMZ001 QD and BID at week 4
- Changes from baseline in WOMAC pain weight-bearing score (questions 1, 2, and 5) and non-weight bearing score (questions 3 and 4) between groups receiving AMZ001 QD and BID at week 4
- Changes from baseline in physical function assessed by the chair-stand test between AMZ001 QD and BID at week 4
- Changes from baseline in WOMAC total score and the WOMAC function and stiffness scores between AMZ001 QD and BID at week 4.
- Changes from baseline in the impact of OA on daily living as assessed by the Patient Global Assessment (PGA) score at week 4

Protocol ID  
AMZ001-006  
Version 1.2

22NOV2018

- 
- Changes from baseline in work productivity and activity assessed by the WPAI at week 4
  - Changes from baseline in quality of life assessed by the EQ5D at week 4

Exploratory endpoints and safety and tolerability endpoints are discussed in [Sections 8.3.4](#) and [8.3.3](#) of the protocol, respectively.

Protocol ID  
AMZ001-006  
Version 1.2

22NOV2018

---

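### When an employed subject worked no hours and lost hours to health, the WPAI missing-item rule read literally discards an overall work impairment score that the SAP's own formula fixes at 100%, if question 5 is blank

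*SAP*

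**What the plan says.** The Protocol synopsis lists among the secondary endpoints: "Changes from baseline in work productivity and activity assessed by the WPAI at week 4". SAP 4.2.3.1 gives the items that matter here as "2 = hours missed due to health problems", "3 = hours missed other reasons", "4 = hours actually worked" and "5 = degree health affected productivity while working (0-10 11-point NRS". Percent work time missed is Q2/(Q2+Q4). Overall work impairment is Q2/(Q2+Q4) + [1 − Q2/(Q2+Q4)] × Q5/10. Both are multiplied by 100.

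The missing-item rule follows: "If any of the WPAI questions required to calculate a given WPAI outcome is missing, no data imputation will be performed", and the outcome is set to missing. No exception is made for a subject who worked no hours. Later in the same section, on excluding implausible hours, the SAP says that the items unaffected by reported hours are kept: "i.e. questions 1, 5 - if applicable - and 6) will not be excluded from analysis". The documents contain no skip instruction for Q5 and do not say how it is recorded when Q4 = 0.

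Under SAP 4.2.3.2 the outcome is analysed as change from baseline in the mITT set, with the same kind of repeated-measures model as the primary endpoint. The WPAI is collected at baseline and weeks 1, 2 and 4.

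**The concern.** A rule against imputing missing items is reasonable when the missing item could change the result. Here it cannot. For an employed subject who lost hours to health and worked none, Q2 and Q4 alone determine overall work impairment. Scoring that subject requires no guess, so it is not imputation in any real sense.

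The loss is tied to the outcome, because it can occur only when the true score is the scale maximum. A mixed model that assumes data are missing at random does not repair this. It relies on the subject's other visits and covariates, and these will generally point to a value below 100%.

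The SAP also follows the opposite principle elsewhere in 4.2.3.1. For the OMERACT-OARSI criteria, a response already settled by the available components is kept, and it becomes missing only if the absent component could change it.

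**Working it through.** There is no stated figure to reproduce, so the check evaluates the SAP's own formula and rule.

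**Inputs from SAP 4.2.3.1:** Q2 = hours lost to health, Q4 = hours worked, Q5 = rating from 0 to 10. Overall = 100 × {Q2/(Q2+Q4) + [1 − Q2/(Q2+Q4)] × Q5/10}.

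**Step 1: no hours worked, some lost to health (Q2 > 0, Q4 = 0).** Q2/(Q2+0) = 1, so overall = 100 × {1 + (1 − 1) × Q5/10} = 100%. Evaluating this for Q2 = 1, 8, 20, 37, 40 and 70 hours, with Q5 at every value from 0 to 10, gives 100% each time. With Q5 missing, a literal calculation returns missing.

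**Step 2: some hours worked.** Q5 does matter here, and the missing-item rule is right.

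| Q2 | Q4 | Q5 = 0 | Q5 = 10 |
|---|---|---|---|
| 20 | 20 | 50% | 100% |
| 32 | 8 | 80% | 100% |

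**Step 3: no hours worked and none lost to health (Q2 = Q4 = 0, for example a week away for other reasons, Q3 only).** The formula is 0/0. Overall work impairment and percent work time missed are both undefined, not 100%. The SAP does not mention this case.

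**Step 4: what the loss does to a change-from-baseline analysis.**
- *After baseline:* one visit with the maximum score drops out.
- *At baseline:* no change can be computed at any visit, so the subject leaves this analysis altogether. If the later score were 25% (assumed), the lost change would be 25 − 100 = −75, a large improvement.

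The two cases pull in opposite directions.

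**Step 5: possible size, on assumed inputs.** The documents do not give the number employed, the number affected or the mean score. Let n = employed subjects in an arm including those affected, k = affected subjects with Q5 blank, and m = mean of the others. Keeping the affected subjects raises the arm's raw mean at that visit by (k/n) × (100 − m).
- n = 90, k = 1, m = 40: (1/90) × 60 = 0.7 points.
- n = 60, k = 2, m = 30: (2/60) × 70 = 2.3 points.
- n = 30, k = 3, m = 20: (3/30) × 80 = 8.0 points.
- k = 0: no shift.

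These are unadjusted means in one arm at one visit. They are not treatment differences from the planned model.

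**The case against.** **The blank Q5 is inferred.** If Q5 is answered, the 100% is kept and nothing is lost. The SAP's remark that Q5 may not be applicable sits beside Q1, the employment item, and could mean only that it does not apply to people without a job. This stands as a limit. A blank remains plausible because the item concerns productivity at work and these subjects did none.

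**An item with zero weight may not count as required.** On that reading the rule does not reach Q5 when Q4 = 0. This is arguable, but the text does not say so. SAP section 5 has a second programmer derive the efficacy endpoints independently, and the two could code it differently.

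**A reader might infer that everyone employed who missed a whole week is affected.** The documents do not support that. Where the hours were missed only for other reasons, the formula is undefined.

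**A reader might infer that the loss dilutes a true benefit by a definite amount.** That would require more absences on placebo than on active gel, all after baseline. The documents give no such counts, similar absences in the arms would largely cancel, and losses at baseline can act the other way.

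**Scoring 100% could let in misreported hours.** The SAP itself records concern that some subjects misunderstood Q2 to Q4. This is a real but limited cost: percent work time missed already scores the same subjects at 100% from the same two items.

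**Full-week absence may be rare.** Subjects must be in reasonably good health apart from osteoarthritis and attend weekly visits. This is fair, and it is why the point is minor.

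**Conclusion.** The point holds in a conditional form. For an employed subject with Q2 > 0, Q4 = 0 and Q5 blank, the rule read literally sets to missing a value that the SAP's formula fixes at 100%. The algebra is exact. How often this happens rests on the inference that Q5 goes unanswered and on absence counts that the documents do not give.

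The loss is informative, but its net direction is not determined. Its size cannot be computed from the documents; it may be zero and is probably small. The range of 0.7 to 8.0 points describes assumed inputs only. One of four WPAI scores under one secondary endpoint is affected. The primary endpoint is untouched.

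A reader might also count it as a defect that percent work time missed and overall work impairment would then cover different subjects. That alone is not one, since the WPAI scores already draw on different items and have different denominators.

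**What to change.** Before unblinding, add to the WPAI derivation in SAP 4.2.3.1:
- If Q1 = yes, Q2 > 0 and Q4 = 0, overall work impairment is 100% regardless of Q5. Impairment while working is left missing for that visit as not applicable.
- If Q2 = Q4 = 0, percent work time missed and overall work impairment are both missing, because the formula is 0/0.
- Otherwise the missing-item rule stands unchanged.

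The cost is a short addition to the text and about one line of code, with no new data. The one downside is that a misreported Q2 or Q4 would enter overall work impairment as 100%, as it already does for percent work time missed. The SAP's existing exclusion of implausible hours should be applied first, so that excluded hours do not trigger the new rule.
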